8.5 Missing Data

For the subjects who have missing value of lung function at the visit, the missing value will be imputed by the mean value calculated based on the subjects with valid observations at the visits, assuming a similar rate of FVC decline with the other subjects. The lung function at baseline will not be imputed. The missing value will be imputed from the first follow-up visit to the last follow-up visit of the subjects.

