8.4 Covariates and Subgroups

Subgroup analysis will be conducted based on the prescription of nintedanib and pirfenidone. All enrolled subjects will be grouped as “no anti-fibrotic drugs” and “with anti-fibrotic drugs”. Subject had no record of anti-fibrotic drugs during the observation will be categorized as “no anti-fibrotic drug”. In contrast, the subjects with at least one record of anti-fibrotic drugs will be categorized as “with anti-fibrotic drugs”.

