9 SUMMARY OF STUDY DATA

All the statistical analysis will be performed and categorized by the subgroup of with anti-fibrotic drug and no anti-fibrotic drug. The summary tables will be tabulated with columns of the two subgroups. The relevant population size will be annotated in the tables.

Continuous variables will be summarized by descriptive statistics: number of observations, mean, median, standard deviation, range, and 95% confidence interval. Frequency counts and percentages of observed levels will be reported for categorical variables. The denominator of percentages will be the number of subjects with valid assessment results. Subjects with missing data will not be included in the number of denominator.

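### SAP 8.5 does not restrict the fill-in mean for missing lung function to the subject's own anti-fibrotic group, although SAP 9 reports all analyses by that group

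*SAP*

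**What the plan says.** SAP 8.5 gives the rule for a subject without a lung function value at a visit: "the missing value will be imputed by the mean value calculated based on the subjects with valid observations at the visits". The reason given is "assuming a similar rate of FVC decline with the other subjects". Neither phrase names a subgroup. Two limits follow: "The lung function at baseline will not be imputed", and "The missing value will be imputed from the first follow-up visit to the last follow-up visit of the subjects".

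SAP 8.4 divides subjects by whether any anti-fibrotic drug was recorded during observation. SAP 9 then states: "All the statistical analysis will be performed and categorized by the subgroup of with anti-fibrotic drug and no anti-fibrotic drug". It adds: "The summary tables will be tabulated with columns of the two subgroups".

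SAP 10.2 defines annual decline as follow-up value minus the subject's own visit 1 value, scaled to a year. It also asks for the level and the change at each visit. SAP 11.1 and 11.3 test annual decline against zero.

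**The concern.** On the plain reading, there is one fill-in mean per visit, taken over everyone with a valid value. A gap in an untreated subject is then filled partly from treated subjects, and the reverse. The imputation treats the two groups as alike, while the tables are built to show each one separately.

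The rule is likely to be used often. Lung function is scheduled at nine follow-up visits (Protocol Table 1), but it is recorded only if done in routine care. Protocol 9.9 names lack of data as a limitation. The variables affected are the primary endpoints: FVC, DLco, SpO₂, TLC and IC all count as lung function in the schedule's footnote. At stake is whether each column describes its own patients.

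**Working it through.** **Inputs.** The documents give no missing fraction, group split, baseline level or rate of decline, so there is no planned figure to reproduce. The following are assumptions: missingness unrelated to lung function within a group; missing fractions of 10-40%; true one-year changes of -3 (drug) and -6 (no drug) points % predicted; and the baselines shown below. From the SAP come the fill rule (8.5), the unimputed baseline (8.5), the change formula (10.2) and the two columns (9).

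**Visit means.** Let F_T and F_U be the true follow-up means with and without drug, m_T and m_U the missing fractions, and q the treated share of observed values. The fill-in mean is P = q·F_T + (1-q)·F_U.

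- Treated column: (1-m_T)·F_T + m_T·P = F_T - m_T(1-q)(F_T-F_U)
- Untreated column: (1-m_U)·F_U + m_U·P = F_U + m_U·q·(F_T-F_U)
- Share of the difference kept: 1 - m_T(1-q) - m_U·q

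With equal missingness m this is 1-m, that is 90%, 80%, 70% or 60% at 10%, 20%, 30% or 40%. With 20% missing in treated subjects, 40% in untreated and 60% treated, q = 0.48/(0.48+0.24) = 0.667. The share kept is then 1 - 0.2×0.333 - 0.4×0.667 = 0.667.

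**Change from baseline.** Baselines are not filled. With equal m, the group difference in change becomes (true difference in change) - m·(F_T-F_U). At m = 30%, for a visit about one year after baseline, with differences taken as drug minus no drug:

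| Baselines drug/no drug | True follow-up means | F_T-F_U | Difference in change after filling (true 3.0) |
|---|---|---|---|
| 75/75 | 72/69 | 3 | 3 - 0.3×3 = 2.1 |
| 70/80 | 67/74 | -7 | 3 - 0.3×(-7) = 5.1 |
| 80/70 | 77/64 | 13 | 3 - 0.3×13 = -0.9 |

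**Within one column.** Take baselines 80/70 with a 70:30 split. P = 0.7×77 + 0.3×64 = 73.1. The treated column gives 0.7×77 + 0.3×73.1 = 75.83, an apparent change of -4.17 instead of -3. The untreated column gives 0.7×64 + 0.3×73.1 = 66.73, an apparent change of -3.27 instead of -6.

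**Simulation check.** With 4,000 replicates, a 70:30 split, 30% missing and assumed SDs of 15 (baseline) and 8 (change), the difference in change came out at 2.10, 5.10 and -0.92. Filling with the mean of the subject's own group instead gave 3.03, 2.91 and 3.07.

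**If a pooled mean change were imputed.** The bias left is m times the group difference in decline, shared between the columns. For a 3-point difference, m = 30% and 60% treated, the treated column moves by 0.3×0.4×3 = 0.36 points and the untreated by 0.3×0.6×3 = 0.54.

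**Spread.** When n values include n_obs observed and the rest set to the observed mean, the SD is multiplied by √[(n_obs-1)/(n-1)]. For n = 100 with 30% filled this is √(69/99) = 0.835, and the SE is 0.70 of the observed-only SE. This applies to visit values, and to changes if a mean change is filled in.

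**The case against.** Section 8.5 never says that the mean is pooled. SAP 9 could be read as making every step group-specific, imputation included. The study is descriptive: SAP 8.7 disclaims any aim of showing differences between treatment groups, the tests are one-sample, and Protocol 9.9 allows stratified analyses to be dropped. Much of the bias in decline also comes from filling in a level rather than a change. If that were corrected, the part due to pooling would be small, and zero if the groups declined equally.

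Some of this stands. Pooling is inferred from wording that names no group, but a programmer following 8.5 as written would pool, so the sentence needs settling either way. The lack of a between-group test limits the harm without removing it, because each column's mean, interval and test against zero still contains the other group's values. The overlap with level versus change is real, yet a pooled mean change still leaves a bias wherever the declines differ.

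A reader might infer three stronger things that the documents do not support:

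- **The columns always move together.** This is true of visit means. It is not true of annual decline, because 10.2 subtracts an unimputed baseline. Treatment is at the physician's discretion, so equal baselines cannot be assumed.
- **The smaller group is always distorted most.** This needs similar missingness. With 60% treated and 40% missing in treated against 10% in untreated subjects, observed shares are equal (0.36 each). The shifts are 0.4×0.5 = 0.20 and 0.1×0.5 = 0.05 of the difference, so the larger group moves further.
- **Results appear only in the two columns.** SAP 9 does not rule out a total column, and the mock-up tables are not part of the documents.

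**Conclusion.** The point holds for the columns by anti-fibrotic group. Differences in visit means shrink by a known factor. Group-specific declines are biased in a direction set by the baselines, and the group difference in decline can narrow, widen or change sign. The factor follows from the rule itself, given missingness unrelated to lung function within each group. The sizes rest on assumed missing fractions, baselines and declines. The annual-decline figures further assume that the follow-up value entering the SAP 10.2 formula is a filled one in the stated fraction of subjects. The harm is to the descriptive columns and the one-sample tests within them, not to a planned treatment comparison. It deserves correction before the database is locked.

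**What to change.** In SAP 8.5, replace the mean fill with a mixed model or multiple imputation that includes the subject's own baseline, anti-fibrotic group, visit and group-by-visit. Report an observed-data analysis alongside.

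If simple imputation is kept, add the same group's mean change from baseline at that visit to the subject's own baseline. Leave the value missing where the group has too few observed values, with the minimum number set in advance. State that the SD and SE are understated, since any single-mean fill has that effect.

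No new data are needed, because the group label is known for every subject at lock. The cost is a rewritten paragraph, somewhat more analysis work, and group estimates that rest on fewer observations than a pooled mean. Neither option removes bias if subjects with worse lung function are more often missing for reasons that the recorded data do not capture.

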9.7.1 Main analysis

The analysis for primary and secondary outcomes, including results of spirometry tests, SGRQ, CAT, and 6MWT will be conducted on the basis of continuous variables, with number, mean (for annual change/decline from baseline, one mean annual change over the whole study period [0-2 years as maximum] will be presented), standard deviation, minimum, Q1 (lower quartile), median, Q2 (upper quartile), maximum value, and 95% confidence intervals included. Wilcoxon Signed Ranked test or t-test, whichever is applicable, will be used to test the change from baseline under a significant level of 0.05.

Time to first acute exacerbation and mortality will be analyzed by Kaplan-Meier estimates, with incidence and time to event included. Time to first acute exacerbation starts from the date of enrolment to the date of first acute exacerbation recorded on the CRF. Patients with exacerbation free at the time of the last contact will be censored. The time of event data will be analyzed using Kaplan-Meier curves. The median, range, and 95% CI for median time and will be reported. Time to death is calculated from the date of enrolment to the date of death from any cause. Patients with no documented death will be censored at the last time they were known to be alive at the time of the last contact. The time of event data (overall survival, censored at 100 weeks) will be analyzed by Kaplan-Meier survival method. The median, range and 95% CI for median survival time and survival curve will be reported.

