1. Age, gender, race, education level, environmental/occupation exposures, height, weight, and BMI.
2. HRCT, surgical lung biopsy, multidisciplinary team (MDT) diagnosis, and UIP pattern.
3. Cough, dyspnea, fatigue, weight loss, dizziness, chest pain, anxiety, aching muscles and joints, clubbed fingers, require oxygen therapy (device), or others (according to physicians' judgment and should be specified on the CRF)
4. STOP-Bang Scoring Model data will be collected to assess if patients have obstructive sleep apnea, and Berlin questionnaire results will only be collected from those with suspected/confirmed obstructive sleep apnea according to STOP-Bang Scoring Model.
5. Concomitant medications used for treating comorbidities within 6 months prior to enrolment will be collected.
6. Anti-fibrotic drugs (i.e., nintedanib and pirfenidone) used within 6 months before baseline will be recorded.
7. Spirometry data include FVC, DLCO, SpO₂, TLC, IC, etc.
8. OFEV relevant ADR (serious and non-serious), fatal AEs, and pregnancies.
9. Hct, Hb, platelets, RBC, WBC, neutrophils, lymphocytes, monocytes, eosinophils, basophils, CRP, CK, rheumatoid factor, antinuclear Ab, anti-Jo1 Ab, Sjogrens SS-A or SS-B Ab, scleroderma-70 Ab, c-ANCA, and p-ANCA, etc..
10. PDGF, VEGF, FGF, etc..
11. MUC5B, etc..

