10.2 Primary Endpoint(s)

- Annual percentage of decline from baseline in FVC

Values of FVC (% pred.) will be used for this endpoint. The FVC(% pred.) collected at visit 1 will be served as baseline.

- Annual decline from baseline in DLco

Values of DLco (% pred.) will be used for this endpoint. The DLco (% pred.) collected at visit 1 will be served as baseline.

- Annual decline from baseline in resting and exercise SpO₂

Values of SpO₂ (%) will be used for this endpoint. The SpO₂ (%) collected at visit 1 will be served as baseline.

- Annual percentage of decline from baseline in TLC

Values of TLC (% pred.) will be used for this endpoint. The TLC (% pred.) collected at visit 1 will be served as baseline.

- Annual percentage of decline from baseline in IC

Values of IC (% pred.) will be used for this endpoint. The IC (% pred.) collected at visit 1 will be served as baseline.

Annual percentage of decline and annual decline from baseline will be calculated as

$$\text{Annual decline} = \frac{\text{Value}_{\text{follow-up}} - \text{Value}_{\text{baseline}}}{\text{Days of follow-up}} \times 365.25$$

In addition to the annual decline, the mean value and mean change from baseline will also be presented for the lung functions. Descriptive statistics including Number, Mean±SD, Median, Range and 95% C.I. of mean value and mean change from baseline at each visit will be calculated and listed.

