11.3 Primary Endpoint Analysis

Annual declines will be summarized with descriptive statistics including Number, Mean \pm SD, Median, Range and 95% C.I. Annual decline will be tested by paired t-test to show if significant change. The Wilcoxon sign rank test will be used if the normally distributed assumption is violated. The test is two sided and the significant level is set as 0.05. The sas procedure used for the tests is listed as follow.

Statistical Test	SAS procedures and option
Shapiro-Wilk test	PROC UNIVARIATE NORMALTEST
T-test	PROC UNIVARIATE MU0=0 ALPHA=0.05
Wilcoxon sign rank test	PROC UNIVARIATE MU0=0 ALPHA=0.025

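### SAP 8.5, read literally, fills a missing lung-function value with the visit mean level while assuming a similar rate of decline, so each imputed change from baseline carries an offset that the assumption rules out

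*SAP*

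**What the plan says.** SAP 8.5 states that a missing lung-function value at a visit is "imputed by the mean value calculated based on the subjects with valid observations at the visits, assuming a similar rate of FVC decline". Baseline is not imputed. On which visits are filled, it adds: "The missing value will be imputed from the first follow-up visit to the last follow-up visit of the subjects".

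The rule covers lung function as a whole. Footnote 7 to the schedule in SAP 7.1.1 begins "Spirometry data include FVC, DLCO" and continues with SpO2, TLC and IC. The assumption names FVC only.

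SAP 10.2 measures change against the patient's own starting value: "The FVC(% pred.) collected at visit 1 will be served as baseline", and likewise for the other measures. Annual decline is follow-up value minus baseline value, divided by days of follow-up, times 365.25. In addition, "mean value and mean change from baseline at each visit will be calculated and listed", with SD, median, range and 95% CI. Protocol 9.7.1 says that "one mean annual change over the whole study period [0-2 years as maximum] will be presented". SAP 11.3 adds a test: "Annual decline will be tested by paired t-test to show if significant change". None of these sections says which follow-up value enters the annual decline, or whether it may be an imputed one.

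**The concern.** A similar rate of decline means that a patient with a missing test changed by about as much as the others did. Giving that patient the others' mean level means something else: that the patient now sits at the group average, wherever he or she began. A patient who started well below average is recorded as improving, and one who started well above as collapsing.

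The protocol abstract calls the study essentially descriptive, and lung function is its primary outcome, so the reported changes and their intervals are the product. Protocol 9.2.3 requires no tests beyond routine care and protocol 9.9 names lack of data as a limitation, so the rule could matter in practice. How often it would be used cannot be read from the documents.

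**Working it through.** The documents give no expected decline, SD or missing rate, so there is no planned figure to reproduce. The algebra needs none of these.

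**1. One patient.** Imputed change = observed patients' mean at the visit − own baseline = observed patients' mean change + (observed patients' mean baseline − own baseline). The bracket is the offset; a similar rate would make it zero.

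Illustration: observed patients average 75 at baseline and 66 at the visit, a change of −9.
- Own baseline 50: 66 − 50 = +16, that is −9 + (75 − 50).
- Own baseline 90: 66 − 90 = −24, that is −9 + (75 − 90).
- The stated assumption gives −9 for both.

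**2. Mean change at a visit.** Averaging over all patients, shift = share missing × (mean baseline of observed − mean baseline of missing). With a 4-point gap and 10% missing: 0.10 × 4 = 0.4 points. With a 13-point gap and 30% missing: 0.30 × 13 = 3.9 points. If the missing patients started higher, the sign reverses.

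**3. Whether imputed values reach the tables.** No section keeps them out. The sentence "Subjects with missing data will not be included in the number of denominator" in SAP 9 concerns the denominators of percentages, not means, SDs, intervals or tests.

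**4. Coverage, by simulation.** Assumed, not from the documents: one pooled group of 100 (the planned N), baseline 75 with SD 15, slope −5 per year with SD 6 and independent of baseline, test error SD 4, t-based 95% CI, 5,000 runs per case. Week 52 is 364/365.25 = 0.997 years, so the true change is −5.0.

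| Week 52 case | Rule: mean change | Rule: coverage | Observed cases: mean change | Observed cases: coverage |
|---|---|---|---|---|
| 5% missing, completely at random (MCAR) | −5.0 | 94% | −5.0 | 95% |
| 30% missing, MCAR | −5.0 | 89% | −5.0 | 95% |
| 10% missing, 4-point lower baseline | −4.6 | 91% | −5.0 | 95% |
| 30% missing, 13-point lower baseline | −1.3 | 17% | −5.2 | 94% |

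In the 30% MCAR case the rule reports a standard error of 1.09, while the true one is about 1.38; observed cases have 0.98. Imputing therefore loses precision against doing nothing, and the interval does not show the loss. Observed cases drift slightly below −5.0 in the last row because missingness was tied to the measured baseline, which contains test error.

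**5. Annual decline.** If the follow-up value is an imputed Week 100 value, the shift is divided by 700/365.25 = 1.916 years. With 30% missing and a 13-point gap: 0.30 × 13 / 1.916 = 2.0 per year, so about −3.1 is reported where observed cases give −5.1. If the last measured value is used, the rule does not touch the annual decline.

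**The case against.** Several points can be made in defence of the plan.

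- **The wording may be loose.** Since the rule is justified by a rate, mean value might have been meant as mean change, and then there is no offset. SAP 10.2 also does not repeat that its per-visit tables use imputed values. A reader might infer that those tables are distorted on any reading; the text does not support that. It takes the literal reading of SAP 8.5 and tables built on imputed values. Both are natural, and neither is confirmed.
- **The primary endpoint may be untouched.** A reader might infer that the annual decline is biased. SAP 10.2 presents the per-visit changes as an addition to the annual decline and leaves the follow-up value of the latter undefined. SAP 8.5 imputes through the last follow-up visit, so an imputed value could enter, but nothing says that it does.
- **A biased mean needs a premise.** A reader might infer that decline will be understated. That requires missing patients to have started lower, and no passage says so. If missingness is unrelated to baseline, the mean is unbiased; if they started higher, decline is overstated.
- **Missingness may be modest.** Protocol 9.9 promises efforts to limit it, and protocol 9.2.3 says that the schedule probably mirrors routine care. With 5% missing at random the damage is slight.
- **The simulation is not the planned table.** SAP 9 splits every table by anti-fibrotic use, and SAP 8.5 does not say whether the imputed mean is pooled or taken within subgroup.
- **Observed cases are no cure for informative missingness.** With 30% missing tied to the patient's own slope, the rule and observed cases both give −3.5 per year.

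All of this stands as a limit on size and certainty. None of it reconciles a level with a rate, and if mean change was intended, the wording still has to be corrected.

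**Conclusion.** The mismatch between rule and assumption is in the text of SAP 8.5, and the offset follows from it together with SAP 10.2. No assumed figure is needed for that.

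The consequences are conditional. Per-visit mean changes are affected if the rule is applied as written and feeds those tables: shifted by share missing × baseline gap where missingness is related to baseline, and otherwise unbiased but less precise than observed cases, with intervals that cover too rarely. The annual decline is affected only if an imputed follow-up value is allowed.

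The illustrative Week 52 range runs from 94% coverage and no bias (5% missing at random) to −1.3 reported for −5.0 with about 17% coverage (30% missing, 13-point gap). It rests on the assumed SDs, slope, missing rates and a single pooled group, and does not predict this study's results.

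**What to change.** SAP 8.5: delete the mean-value imputation. State that missing follow-up lung-function values are not imputed; that summaries, intervals and tests use observed values at the actual test date; and that the number observed is shown for each visit and subgroup.

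SAP 10.2: state that the annual decline uses a measured follow-up value, for example the last one, and that days of follow-up run to the date of that test.

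Optional, as support only: a random-intercept, random-slope mixed model on all observed values, or multiple imputation conditional on own baseline and earlier values. The mixed model assumes linear decline and does not itself give the per-patient SD, quartiles or signed-rank test of protocol 9.7.1, so it cannot replace the observed-value summaries.

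Rewording the rule to own baseline plus mean observed change would match the assumption and remove the offset. As a single imputation it would still understate the standard error, with about 82% coverage at 30% missing at random, so it is only a partial repair.

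Cost: SAP wording, with no new data. The price is a smaller number of patients per visit and noisy annualised values from early exits. The SAP should state as a limitation that none of these methods removes bias if missingness depends on unseen decline.

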8.6 Interim Analyses and Data Monitoring

There is no planned interim analysis in protocol.

8.7 Adjustments for Multiplicity

The study was not aimed to show significant difference between treatment groups and no hypothesis testing will be performed. Hence there is no need to adjust for multiplicity.

